**Fig. 8. “Go” criteria: #1, plus at least one of #’s 2, 3 & 4 ( $d > 0.5$ )**

1. **Target engagement:** APS learning, AMPH > PBO,  $p < 0.05$
2. **Greater clinical, neurocognitive or functional gains:**
  - $\downarrow$ PANSSt,  $\uparrow$ MCCB-C or  $\uparrow$ Fnxn: AMPH+TCT > PBO+TCT
3. **Faster clinical, neurocognitive or functional gains:**
  - drug group x session interaction ( $p < 0.05$ ) followed by AMPH+TCT > PBO+TCT at specific session # or combination;
4. **More durable** clinical, neurocognitive or functional gains:
  - AMPH+TCT > PBO+TCT at post-TCT week 12.

PANSSt: Positive & Negative Symptom Scale total; MCCB-C: MATRICS Composite; Fnxn: Function (assessed via the World Health Organization Disability Schedule 2.0 (WHODAS))

**Outcome and “Go Decisions”.** In addition to confirming “target engagement”, this application tests the hypothesis that SZ patients given AMPH +TCT will exhibit greater, faster and/or more durable improvements (change from baseline) in symptoms, neurocognition and/or function compared to patients given PBO+TCT, and that this enhanced clinical response will be associated with greater AMPH-enhanced TCT learning.

The small “n” necessitated by the 3-year timeline and demanding treatment schedule greatly constrains the total number of outcome measures.

Moreover, the plan to assess not only magnitude but also rate and durability of PACT gains triples the number of primary analyses. Thus, we selected only one **primary** clinical, neurocognitive and functional outcome measure (Fig. 8) – recognizing that they are relatively “blunt” metrics - but will track several other, more focused, measures as well as inter-measure correlations in exploratory analyses to inform future studies.

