**Aim 2 – Test clinical, neurocognitive and functional impact of AMPH on TCT, and its relationship to target engagement:** We will determine if AMPH+TCT produces greater, faster or more durable clinical, neurocognitive or functional gains from baseline, compared to PBO+TCT, over a 30-session course of TCT. A Cohen’s  $d \geq 0.5$  for the main effect of drug (PBO vs. AMPH) or drug x session (#10, 20, 30) interaction in an LME model is the primary “Go” criteria. The main effect of drug assesses “greater” gains. Reverse Helmert contrasts for session assesses “faster” gains. A separate model comparing differences in outcomes at 12-weeks post-TCT assesses “more durable” gains. Secondary regression analyses will examine whether change in AMPH-enhanced APS learning (“within-subject” target engagement; Aim 1) predicts gains in Aim 2 outcome measures.

**Aim 3 – Biomarkers of AMPH-induced gains:** We will determine if baseline levels of specific neurocognitive or EEG-based measures, or changes in specific measures with initial AMPH exposure (Test 2 vs. 1), predict greater sensitivity to AMPH-enhanced neurocognitive, clinical or functional gains over 30-h of TCT. Regression analyses will assess whether specific candidate biomarkers predict AMPH-enhanced gains in outcome measures.

**Subject “throughput”:** We will enroll and screen 23 subjects/yr, test target engagement in 18 subjects/yr, and (conservatively) complete TCT training in 12 subjects/yr. This will yield 2 “target engagement” Aim 1 arms of  $n=27$ , and (conservatively) 2 TCT completion Aim 2 arms of  $n=18$ . Training capacity (2 TCT stations with morning and afternoon sessions on M, W and F, with T and Th “make-up” days for missed appointments, 48 weeks/year) allows for a “maximum throughput” of 19.2 subjects/yr. To reach the target of **12 TCT-completing subjects /year**, we would need to maintain training rates of **62.5% capacity**. This is well within our historical testing levels.

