Analyses testing primary and secondary hypotheses will include all subjects' clinical, neurocognitive and functional assessments. Data from subjects who do not complete the full study are carried forward in an "intent to treat" design, and their data are analyzed using linear mixed models. Separate analyses will compare completion / drop-out rates across arms, as well as a 14-item 7-point Likert scale assessing treatment satisfaction.

Go/No-Go decision and primary and secondary endpoints

"Go/No-Go" decisions are based on traditional statistical significance (Aim 1) and effect sizes (Aim 2). Formal statistical testing is conducted using linear mixed-effects (LME) models; hypothesis tests are 2-sided ($\alpha=.05$). Model parameters are estimated via the R lme4 package and Cohen's d is estimated via the EMATools package. Type I errors are minimized by constraining the number of primary analyses; secondary analyses use false discovery rate corrections.

PANSSt scores will be assessed at specific intervals. **It is important to emphasize that the anticipated symptomatic gains will reflect an enhanced impact of TCT, rather than a direct therapeutic impact of AMPH (5 mg, 2-3 times per week).** Because TCT is associated with improvements in both positive and negative symptoms, our *a priori* hypothesis is that a PACT effect will be evident in both positive and negative symptoms. Hence, PANSSt is used as the primary metric of symptomatic gains. A greater reduction in PANSSt score will be detected using data from baseline through TCT 30h, by a significant main effect of group (arm) or a significant interaction of group x session, with post-hoc contrasts revealing significant group differences at TCT 30h. A faster reduction in PANSSt scores will be detected using these same data by a significant interaction of group x session and a significant group difference at a point prior to TCT 30h. A more durable reduction in PANSSt scores will be detected using data from TCT 30h through 12 weeks post-TCT, by a significant main effect of arm or a significant interaction of group x post-TCT day, with post-hoc contrasts revealing significant group differences 12 weeks post-TCT.

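### The protocol's Aim 2 contrast for *faster* gains cancels any drug effect already present at session 10, and Fig. 8 and the SAP each define *faster* differently

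*Protocol*

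**What the plan says.** Three places define *faster*, and a fourth leaves it out.

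- **Protocol, Data Analysis, Aim 2.** The outcome is "clinical, neurocognitive or functional gains from baseline, compared to PBO+TCT, over a 30-session course of TCT". A d of at least 0.5 on the main effect of drug, or on the "drug x session (#10, 20, 30) interaction in an LME model is the primary" Go criterion. The main effect stands for *greater*; "Reverse Helmert contrasts for session assesses" *faster*. Baseline is not among the listed session levels, and the interaction is given no direction.
- **Protocol, Fig. 8, criterion 3.** An interaction at p<0.05, "followed by AMPH+TCT > PBO+TCT at specific session # or combination". The figure's title adds d above 0.5. Nothing requires the session to be an early one.
- **SAP, Go/No-Go decision.** The rule for *greater* opens "A greater reduction in PANSSt score will be detected using data from baseline through TCT 30h". The rule for *faster* takes over that data window and is met "by a significant interaction of group x session and a significant group difference at a point prior to TCT 30h". This is spelled out for PANSS total only. MCCB and WHODAS are to be handled comparably, with a reference back to the Research Strategy, which is where the other two rules stand.
- **SAP, Project Modification.** It describes a between-group interaction model, effect sizes for the change from baseline to P30, and a threshold of 0.4 above placebo. It contains no *faster* contrast and does not say that the criterion was withdrawn.

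**The concern.** Bringing gains forward is a stated purpose of the trial: Aim 2 asks about the rate of gain, and the protocol's discussion of ceiling effects treats acceleration as clinically important. Under Fig. 8, once target engagement is shown, *faster* alone can supply the therapeutic part of a Go.

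A reverse Helmert contrast compares each level with the mean of the levels before it. If session 10 is the first level, no contrast compares session 10 with the start of training, which is where acceleration should show first. The contrasts ask instead whether the arm difference grows after session 10. The same data could also be Go under one of the three rules and No-Go under another.

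**Working it through.** **Contrast algebra.** Let D10, D20 and D30 be the AMPH minus PBO difference in gain from baseline, in SD units, positive when it favours AMPH. The reverse Helmert interaction contrasts on the Aim 2 levels are

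- C1 = D20 - D10
- C2 = D30 - (D10 + D20)/2

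and the main effect is (D10 + D20 + D30)/3. For the graded pattern, C1 = 0.25 - 0.5 = -0.25 and C2 = 0 - (0.5 + 0.25)/2 = -0.375. For late-only, C2 = 0.5 - 0 = +0.50.

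| Pattern (D10/D20/D30) | C1 | C2 | Main effect |
|---|---|---|---|
| Sustained lead .5/.5/.5 | 0 | 0 | 0.50 |
| Lead, caught up by 30 .5/.5/0 | 0 | -0.50 | 0.33 |
| Graded catch-up .5/.25/0 | -0.25 | -0.375 | 0.25 |
| Early only .5/0/0 | -0.50 | -0.25 | 0.17 |
| Early and growing .5/.6/.7 | +0.10 | +0.15 | 0.60 |
| Late only 0/0/.5 | 0 | +0.50 | 0.17 |

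Only the late-only pattern reaches +0.5 on a contrast.

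**Adding baseline as a fourth level (D0 = 0).** The first contrast becomes D10 - 0 = D10, which is 0.50 for every early pattern and 0 for late-only. The last becomes D30 - (D0 + D10 + D20)/3, still 0.50 for late-only. Baseline alone therefore does not exclude a late-only pass; the SAP's pre-30 h condition does.

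**The plan's own figure.** The only sample-size figure is 27 per group for Aim 1 (d=0.5, 80% power, two-sided 0.05, correlation 0.8). The SD of change is sqrt(2(1 - 0.8)) = 0.632. The normal formula gives 26; the t-test gives 26.1, rounded up to 27, with 81.3% power at 27. The figure reproduces on a change-score reading. The point here does not depend on it.

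**Pass rates by simulation.** From the documents: 18 completers per arm (Recruitment and Retention Plan) and correlation 0.8 (borrowed from the Aim 1 power statement). Assumed: equal correlations between visits, unit SD, complete data, d on the SD of change, 1,500 runs per pattern. Aim 2 is read as signed (larger contrast at least 0.5). Fig. 8 is read as a three-level interaction at p<0.05, then d above 0.5 at some session. The SAP is read as an interaction at p<0.05 with baseline as a level, then a significant favourable difference at session 10 or 20.

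| Pattern | Aim 2 | Fig. 8 | SAP |
|---|---|---|---|
| Sustained lead .5/.5/.5 | 13% | 5% | 64% |
| Caught up by 30 .5/.5/0 | 7% | 64% | 74% |
| Early only .5/0/0 | 0.2% | 60% | 56% |
| Late only 0/0/.5 | 85% | 59% | 4.5% |
| No effect | 10% | 2% | 1% |

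Under Aim 2 the sustained-lead and no-effect rows estimate the same quantity, because a constant difference cancels; 13% against 10% is simulation noise. Varying the SD used for d (raw or contrast SD, 20,000 runs), the Aim 2 rule passes late-only in 50-90%, graded catch-up in 0-0.5%, and both the sustained lead and no effect in 1-14%.

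**The case against.** A reader might infer that the plan as a whole rewards the opposite time course and cannot find acceleration. The documents do not support that.

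- **The SAP rule largely works.** It uses baseline through 30 h and needs a group difference before 30 h. It passes late-only in 4.5% of runs and the early patterns tabulated in 56-74%. It does not share the defect.
- **Fig. 8 can find an early lead that placebo catches.** The protocol's tests are two-sided, so a negative interaction counts; that pattern passes in 60-64% of runs.
- **Near-zero pass rates for catch-up under Aim 2 need a signed d.** The text gives no direction. Read as an absolute value, the .5/.5/0 and early-only patterns reach 0.5. Late-only would still pass, and a sustained lead would still score zero.
- **Zero or negative is not universal.** An early and growing effect scores +0.10 and +0.15, positive but below threshold.
- **A constant difference is arguably *greater*, not *faster*.** The sustained lead has a main effect of 0.50 and can reach Go that way. A true difference at session 30 can also meet the SAP's *greater* rule, so labelling it *faster* is not necessarily a wrong Go.
- **The Project Modification may have retired the criterion.** It lists no *faster* contrast, though it does not withdraw one.

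All of this stands and narrows the point. It does not rescue the Aim 2 contrast, which has no sensitivity to a head start that is held. Nor does it reconcile Fig. 8, which accepts a session-30-only difference and, on the Aim 2 session levels, detects a sustained lead no more often than chance.

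**Conclusion.** The Aim 2 rule is wrong as written: on session levels 10, 20 and 30 it does not measure *faster*, and it conflicts with Fig. 8 and the SAP. That follows from the contrast algebra and needs no assumption about correlation or SD. The pass rates do depend on the assumed correlation of 0.8 and on the SD scale, and the plan does not state that scale.

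The consequence for Go is limited. The main loss is an early lead that placebo catches: its main effect is 0.25 to 0.33 in the two catch-up patterns, below 0.5, so under a signed reading Aim 2 misses it both as *faster* and as *greater*. The second consequence is mislabelling, since a late-only effect scores +0.50 and is recorded as *faster*. A sustained lead keeps its route through *greater*. How much of this bears on the final analysis depends on whether the Project Modification kept the criterion, which the SAP leaves open.

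**What to change.** Use one definition of *faster* in Fig. 8, in Data Analysis Aim 2 and in the SAP's Go/No-Go section, for all three outcomes. Define it as the AMPH minus PBO difference in change from baseline at a pre-specified session before 30 (10 and/or 20), with baseline as the reference level. State the favourable direction: lower PANSS total and WHODAS, higher MCCB composite. This replaces the three-level reverse Helmert interaction as the *faster* test.

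State the chance of passing with no drug effect. At 18 per arm, d of 0.5 on the change-score SD is t = 0.5 x sqrt(18/2) = 1.5 on 34 df, about 7% in the favourable tail per comparison. Over three outcomes, if independent, that is 1 - 0.93^3, about 20%, and more if either session may count. The 7% is no worse than the 10% simulated for the Aim 2 rule, but it is above the 1-2% for the SAP and Fig. 8 rules, which also require significance. The authors should choose between them openly. With d taken on the raw or contrast SD, a session-10 rule of this kind passes 50-81% of runs for the sustained and graded catch-up patterns and 1-7% for late-only.

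If the Project Modification dropped *faster*, say so there. The cost is wording and contrast coding; no new data are needed.

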Based on these findings, we submitted an R61/R33 application (MH112742); the primary goal of the R61 was to both confirm “target engagement” (AMPH effects on APS learning) and optimize AMPH dose and post-AMPH time interval for an R33 “pilot” trial of an AMPH/TCT PACT design in SZ patients. The major critiques of this application were that the proposed R61 scope (parametric dose- and time-course optimization) was 1) “incremental” (not novel); and 2) not “significantly distinct from [the scope of] MH59803”. Seeing no other viable path forward, over the next 2 years we used carry-over funds from MH59803 and funds from a NARSAD Distinguished Investigator Award to complete the previously proposed R61 parametric studies (target n=36 SZ patients; current n=30), in addition to relevant “foundational” studies of TCT in SZ patients, described below.

These studies (Fig. 3; reported in) use a within-subject 4-week design to test dose-response effects of AMPH (0, 2.5, 5 or 10 mg po) on APS learning, given 60 (current n=12) or 210 min (n=18) prior to Sound Sweeps. AMPH significantly enhanced APS learning at both time-points, with an inverted-U dose-function reflecting maximal gains with 5 mg ( $d=0.85$ ; Fig. 3A). APS learning gains with AMPH were greatest among patients in the lowest 50% of attention/vigilance (A/V) scores (the highest 50% scored in a “normal” A/V range), consistent with our findings that low baseline attention/ vigilance predicts greatest AMPH-enhanced attention. AMPH-induced gains in auditory discrimination (assessed by the QuickSIN “Speech-in-Noise” measure) and sensorimotor gating (prepulse inhibition) in SZ patients parallel those in APS learning, both in terms of optimal dose (5 mg) and attention-dependence (greatest in patients with low MCCB “A/V” scores) (Fig. 3C,D). We have preliminary evidence for similar findings with memantine, a drug pharmacologically distinct from AMPH, and collectively these findings are incorporated into our working mechanistic models for PACT effects on TCT (e.g. Fig. 1).

[figure not shown]

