**Data Analysis:** “Go/No Go” decisions are based on traditional statistical significance (Aim 1) and effect sizes (Aim 2). Formal statistical testing is conducted using linear mixed-effects (LME) models; hypothesis tests are 2-sided ( $\alpha=0.05$ ). Model parameters are estimated via the R lme4 package and Cohen’s  $d$  is estimated via the EMAtools package. Type I errors are minimized by constraining the number of primary analyses; secondary analyses use false discovery rate corrections. Expected attrition rates are described above. Because outcome measures involve a “change from baseline”, baseline metrics are compared between PBO and AMPH arms, and any baseline differences are addressed in the outcome analyses. Differential drop-out rates from PBO vs. AMPH arms are monitored. Data are assumed to be missing at random; full information maximum likelihood estimators are used, and all data/cases are included in analyses. Clinical follow-up is pursued with all patients exiting the study through post-TCT week 12. Cohort differences: For between-subject contrasts (main effect of drug), differences in age, antipsychotic and anticholinergic loads are tested and used as covariates. Sex differences are tested for all measures based on known sex differences in AMPH sensitivity. NIH Data Harmonization: 3 “PhenX Toolkit” (NOT-MH-15-009) measures of function are used; see above and “Resource Sharing Plan”.

**Aim 1 – Confirm target engagement:** The primary dependent measure of target engagement is AMPH-enhanced APS learning. APS learning is defined as the reduction in Sound Sweeps APS threshold (ms) pre- to post-assessment. Target engagement was demonstrated in MH59803, and will be confirmed if APS learning is increased by AMPH either in a within-subject comparison (AMPH group, “Test 2 vs. 1”), or in a between-subject comparison (AMPH group vs. placebo group change “Test 2” vs. “Test 1”) (note that AMPH and PBO groups are matched by Test 1 PBO performance via stratified randomized assignment). Effect sizes and inferential statistics are based on LME models with random intercepts. A statistically significant main effect of drug (PBO vs. AMPH) on APS learning in either within- or between-subject contrasts is a “Go” criteria and confirms target engagement.

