**Power analyses:** Consistent with the FOA, this study will adequately power tests of target engagement (Aim 1) for traditional significance, while the “Go” signal for therapeutic impact (Aim 2) is based on effect size ( $d=0.5$ ). To detect target engagement with  $d=0.5$ , 80% power,  $\alpha=0.05$ , test-retest correlation =0.8, and a linear treatment effect,  $n=27$  randomized participants are required per group. This is a very conservative estimate of  $d$  for target engagement, since empirically,  $d$  for target engagement with 5 mg amphetamine was 0.85 (Fig. 3A). A future Confirmatory Efficacy trial will be powered to apply more robust approaches to Aim 2, e.g. Path Analysis to study moderating effects of APS AMPH sensitivity and biomarkers on both indirect (moderated-mediation) and direct paths between treatment and outcome.

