General Statistical Approach: Hypothesis tests are 2-sided ($\alpha=.05$). Type I error is controlled by selecting optimal *a priori* targets for primary analyses; secondary analyses use false discovery rate corrections. When appropriate, missing data are handled via multiple imputation or full information maximum likelihood estimation. Expected drop-out rates and ways to minimize them are described in the parent application.

Differential drop-out rates from PBO vs. AMPH arms are monitored. Clinical follow-up is pursued with all patients exiting the study through post-TCT week 12.

Cohort differences: For between-subject contrasts (drug), baseline demographic, clinical, antipsychotic/anticholinergic load and performance differences are tested and used as covariates if indicated. Sex differences are tested for all measures.

Procedures for Alternative or Unexpected Results: Linear mixed-effects models allow for the analysis of all available data using an intent-to-treat approach. This approach, however, assumes that data are missing at random. A potential concern is nonrandom dropout, particularly when dropout is related to the (missing) outcomes; that is, not missing at random. To make the missing at random assumption more plausible, we will explore the use of auxiliary variables. Auxiliary variables are covariates that predict both dropout and outcomes. By adding auxiliary variables to our models, nonrandom dropout is corrected by conditioning treatment effects on the predictors of dropout.

Primary Efficacy Endpoint(s): Aim 1: Target engagement – APS learning will be significantly greater under AMPH vs. PBO conditions. Aim 2: Pilot trial - Compared to PBO arm patients, AMPH arm patients will exhibit greater clinical benefit, as indicated by one or more of the following: greater, faster or more durable improvements in PANSSt (reduced scores; see below, “Go/No-Go”), MCCBc (increased scores) or WHODAS (reduced scores).

Secondary Efficacy Endpoint(s): Aim 3: Biomarkers - baseline levels of specific neurocognitive or EEG-based measures, or changes in specific measures with initial AMPH exposure, predict greater sensitivity to AMPH-enhanced neurocognitive, clinical or functional gains over 30 sessions of TCT.

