Comparable analytic approaches will be used for neurocognition (MCCBc) and function (WHODAS) as described in "Research Strategy". Data will be described as means with SEM. Tests for normalcy will be applied to all data and non-parametric comparisons will be used if normalcy is not demonstrated. The Analysis Set for these data will be all subjects who have completed 30h of TCT and post-TCT clinical, neurocognitive and function assessments. When appropriate, missing data are handled via multiple imputation or full information maximum likelihood estimation.

Secondary regression analyses assess the predictive value of putative biomarkers on clinical, neurocognitive or functional gains from the addition of AMPH to TCT. Future studies with larger samples will assess potentially more informative models, e.g. Path Analysis to study moderating effects of APS AMPH sensitivity and biomarkers on both indirect (moderated-mediation) and direct paths between treatment and outcome.

Power analyses

Consistent with the FOA, this study will adequately power tests of target engagement (Aim 1) for traditional significance, while the "Go" signal for therapeutic impact (Aim 2) is based on effect size ($d=0.5$). To detect target engagement with $d=0.5$, 80% power, $\alpha=0.05$, test-retest correlation =0.8, and a linear treatment effect, $n=27$ randomized participants are required per group. This is a very conservative estimate of d for target engagement, since empirically, d for target engagement with 5 mg amphetamine was 0.85 (Fig. 3A). A future Confirmatory Efficacy trial will be powered to apply more robust approaches to Aim 2, e.g. Path Analysis¹⁰⁸ to study moderating effects of APS AMPH sensitivity and biomarkers on both indirect (moderated-mediation) and direct paths between treatment and outcome.

Project Modification: Statistical Analysis Plan

The original study design included separate, parallel assessments of amphetamine (AMPH) (vs. placebo (PBO)) and memantine (MEM) (vs. PBO) effects on TCT-associated clinical, neurocognitive and functional gains. However, these designs pre-dated the pandemic, and between the date that they were proposed (10/2019) and the project start date (8/2020), our institution implemented a pandemic-related shut-down of clinical research activities. Even with the gradual resumption of research activities, recruitment lagged significantly behind target levels. As a result, we made several pragmatic adjustments to the original study designs:

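### Aim 1's 80% power holds only at an unsourced test-retest correlation of 0.8, and the claim that d=0.5 is very conservative is not supported as written

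*Protocol*

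**What the plan says.** The Power analyses paragraphs of the protocol and SAP give the same calculation: "To detect target engagement with $d=0.5$, 80% power", two-sided alpha 0.05, with "test-retest correlation =0.8, and a linear treatment effect", so that 27 "randomized participants are required per group". The protocol then adds, "This is a very conservative estimate of" d, and the SAP repeats it: "This is a very conservative estimate of d for target engagement". The only reason offered is that the observed d with 5 mg was 0.85, cited to Fig. 3A.

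The endpoint is defined in the protocol under Aim 1 of Data Analysis: "APS learning is defined as the reduction in Sound Sweeps APS threshold (ms) pre- to post-assessment". The study behind the 0.85 is described under Preliminary Studies 1, whose experiments "use a within-subject 4-week design to test dose-response effects of AMPH" at 0, 2.5, 5 and 10 mg. At the time of writing it had 30 patients, 12 tested at 60 minutes and 18 at 210 minutes, and 5 mg was the peak of the dose curve.

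The between-arm contrast is described in two ways. Specific Procedures (TCT) compares the arms at Test 2 alone. Aim 1 of Data Analysis compares the arms on change between Test 1 and Test 2. Aim 1 also counts as a Go if either the between-arm contrast or the within-arm contrast (AMPH arm, Test 2 against Test 1) is significant.

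**The concern.** Target engagement is a required Go criterion (Fig. 8), and the protocol says that if it is not confirmed the setting will be judged unsuitable for detecting AMPH effects on APS learning. That inference needs a defensible false-negative rate.

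Two things make the stated rate look firmer than it is. First, r=0.8 must hold for a pre-minus-post score measured twice, 5 to 7 days apart. The documents give no repeatability, SD or reliability for APS learning; the retest stability cited under Feasibility concerns ERPs and other biomarkers. Second, the comparison of 0.85 with 0.5 assumes both are in the same units. One comes from a within-subject study and the other is standardised for a parallel-group change calculation.

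**Working it through.** **Inputs.** From the documents: d=0.5, two-sided alpha 0.05, r=0.8, 27 per arm, preliminary d=0.85 with n=30. Assumed: values of r below 0.8, since the documents give no estimate. Power uses the non-central t.

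**1. Reproducing 27.** Take d in units of the single-occasion SD of APS learning.
- Change score: SD = √(2(1−r)) = √0.4 = 0.632. Needed: 27 per arm; power at 27 is 81.3%. This matches.
- ANCOVA: SD = √(1−r²) = √0.36 = 0.600. Needed: 24 per arm.
- Test 2 only: SD = 1. Needed: 64 per arm; power at 27 is 44%.

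So the plan's figure is the between-arm change-score calculation.

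**2. Dependence on r** (d=0.5, 27 per arm; 52 df for change, 51 for ANCOVA, 26 for the paired test of 0.5/√(2(1−r))). The last column is the simulated chance that at least one of the change-score and paired contrasts is significant, with no shift from Test 1 to Test 2 apart from the drug effect.

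| r | Change score | ANCOVA | Paired, AMPH arm | Either contrast |
|---|---|---|---|---|
| 0.8 | 81% | 85% | 98% | 98% |
| 0.7 | 64% | 71% | 90% | 91% |
| 0.6 | 52% | 62% | 80% | 82% |
| 0.5 | 44% | 55% | 71% | 74% |

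ANCOVA beats the change score at every r below 1, because 1−r² = (1−r)(1+r) is less than 2(1−r). It beats Test 2 alone whenever Test 1 learning carries information.

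**3. How demanding r=0.8 is for a difference score.** With single-threshold reliability ρ and pre-post correlation c (both assumed), reliability of the difference is (ρ−c)/(1−c).
- ρ=0.8: (0.8−0.5)/0.5 = 0.60 at c=0.5, and (0.8−0.7)/0.3 = 0.33 at c=0.7.
- To reach 0.8: ρ = c+0.8(1−c), which is 0.90 at c=0.5 and 0.94 at c=0.7.

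This illustrates the requirement; it does not estimate r.

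**4. The scale of 0.85.** If it was standardised by the SD of paired differences, its value on the planned scale is 0.85·√(2(1−r)):
- r=0.8: 0.85×0.632 = 0.54
- r=0.7: 0.66
- r=0.6: 0.76
- r=0.5: 0.85

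At the plan's own r, the margin over 0.5 is then 0.54/0.5, about 8%, rather than 0.85/0.5, or 70%. Equivalently, the planned 0.5 is 0.5/0.632 = 0.79 on the paired scale. With n=30 the 95% interval for a paired d of 0.85 is about 0.43 to 1.26, or 0.27 to 0.80 on the planned scale at r=0.8.

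If the true effect is a paired d of 0.85, change-score power at 27 per arm is 86.5% whatever r is. If 0.85 is on the single-occasion scale, power is 99.8% at r=0.8 and stays at or above 80% down to r of about 0.40.

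**The case against.** The strongest reply is that the gate is wider than the between-arm contrast. A reader might infer from the change-score column that a real effect of the planned size would fail Aim 1 about half the time if r were 0.5 or 0.6. The documents do not support that. Either contrast suffices, and with no shift between tests the gate passes about 82% of the time at r=0.6 and 74% at r=0.5. This part of the reply stands. Its limit is that the within-arm route has no control for practice: Test 1 is always on placebo and always first. At r=0.5 a shift of 0.2 SD common to both arms moves the pass rate to 51% if downward and 94% if upward (assumed shifts), so that route says little about the drug. The stated n is not derived from it.

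A second reply is that the two criticisms offset each other. If 0.85 is a paired d, a lower r makes it larger on the planned scale, so d=0.5 becomes more cautious exactly where change-score power at d=0.5 drops. This also stands. A reader might infer that the trial is underpowered, but at its point estimate the pilot effect gives more than 80% power at r=0.8 on either reading of 0.85.

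Third, the standardiser may be given in Fig. 3A or the cited report, neither of which is available here. The Fig. 3 legend reports similar 5 mg effects at 60 and 210 minutes, and a separate study of 24 patients found an effect with 10 mg. These points soften doubts about the pilot; they do not put 0.85 and 0.5 on one scale.

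Fourth, the plan already stratifies on high or low Test 1 learning, uses mixed models, and allows performance covariates where indicated. None of this fixes the analysis. A high/low stratum uses only part of the Test 1 information. A random-intercept model with arm, test and their interaction gives the change-score contrast in complete data. It approaches ANCOVA only if the arms share one Test 1 mean, which the protocol does not state.

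**Conclusion.** The concern holds as a gap in justification, not an error of arithmetic. The 27 per arm is correct for a between-arm change-score test at r=0.8. The 80% is conditional on that unsourced r and falls to 64%, 52% and 44% at assumed r of 0.7, 0.6 and 0.5. The loss concerns the placebo-controlled contrast, which is the one that can attribute learning to the drug; it does not carry over in full to the either-contrast gate. The claim of conservatism rests only on 0.85 exceeding 0.5. The true margin may be anywhere from about 8% (paired d, r=0.8) to 70% (same scale), before allowing for choice of the best dose and a small sample. Underpowering is not shown.

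All figures describe the original 1:1 design with 27 per arm. The SAP's Project Modification section pools placebo groups, moves to 2:1 allocation, reports samples well below target, and does not list APS learning among its three primary outcomes.

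**What to change.** - Specify the Aim 1 between-arm analysis as ANCOVA of Test 2 APS learning on continuous Test 1 APS learning. At 27 per arm and d=0.5 this gives 85%, 71%, 62% and 55% power at r=0.8, 0.7, 0.6 and 0.5. It also replaces the two conflicting descriptions (Test 2 only in Specific Procedures, change in Data Analysis) with one.
- State the 80% as conditional on r=0.8, give the source of that value if there is one, and show power over a range of r.
- State how 0.85 was standardised, with its interval. Delete the claim of conservatism unless 0.85 is converted to the planned scale.
- Say that the 27-per-arm power statement belongs to the original design and not to the modified 2:1 design.

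The cost is wording and a less favourable stated power. ANCOVA uses data already collected, and no change to n is needed.
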